#### 5.2.3 Cannulation Success

Cannulation success is defined as with successful first use for HD using 2-needle cannulation. This endpoint will be evaluated through 6 months. Additionally, for exploratory purposes, the endpoint will be evaluated through 30 days, 6 weeks, 3 months, 12 months, 18 months, and 24 months.

The event of cannulation success will be identified if:

On the EndoAVF Dialysis page, "Date endoAVF First Used with 2 Needles for Hemodialysis" is not NULL and within a specific visit (e.g., within 210 days for 6 months post creation).

Kaplan-Meier (KM) analysis will be used to estimate the time from HD AV access creation (the date of index procedure) to first successful use for HD using 2-needle cannulation through certain post creation visit.

- If cannulation success occurs, the participant is considered as having the event at the corresponding date.
- If the participant was transferred to PDs, or had a kidney transplant, or had access discontinuation, or discontinued before the end of a specific visit window (e.g.180+30 = Day 210 for 6-month visit) without cannulation success, the participant is considered as censored at the earliest date among these events (i.e. PD start date, kidney transplant date, date of access discontinuation, or last date of available study data including the unscheduled visit date).
- Otherwise, if the participant did not achieve cannulation success and has passed the specific visit window by the cutoff date of database lock, the participant will be censored at the end of the reporting time window (e.g., 180+30 = Day 210 for the 6-month reporting, 730+30 = 760 for the 24-month reporting) for this analysis. If the participant had access permanent abandonment prior to achieving cannulation success and has passed the specific visit window by the cutoff date of database lock, the participant will be censored at the date of permanent abandonment.

This endpoint will be evaluated on the AT population. The number of participants with events, number of participants censored, time to event (days), and proportion of participants with events along with the 95% CI will be presented at 6-months post creation using the KM method. For the 6-month reporting, the cannulation success rate up to 6-months (up to Day 210) will be presented. For the final reporting, the cannulation success rate up to 24-months (up to Day 760) will be presented.

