4.2.2 Effectiveness

• Physiological Maturation

The proportion of participants with AVFs that meet the definition of physiological maturation. Physiological maturation is defined as an AVF having at least 500 mL/min of flow in the brachial artery and an outflow vein diameter of ≥ 4 mm as measured by DUS. ^{16,17} Participants with AVFs that meet the definition of functional maturation (Refer to Section 4.3) will automatically meet physiological maturation. This endpoint will be assessed through 6-weeks post creation.

• Cannulation Success

The interval of time between HD arteriovenous (AV) access creation to first successful use for HD using 2-needle cannulation and proportion of participants with successful first use for HD using 2-needle cannulation. This endpoint will be assessed through 6-months post creation.

• Cumulative Functional Patency

The time from first successful HD AV access use for HD using 2-needle cannulation to access abandonment, when the access reaches an access censoring event as specified a priori in this CIP, or analysis timepoint / clinical investigation end. This endpoint will be assessed through 12-months post creation.

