#### **5.2.4** Cumulative Functional Patency

The time interval of cumulative functional patency is defined as the time from first successful HD AV access use for HD using 2-needle cannulation to access abandonment. This endpoint will be evaluated through 12-months. Additionally, for exploratory purposes, the endpoint will be evaluated through 6 months, 18 months, and 24 months.

Only the participants who have started 2-needle HD using the endoAVF will be considered as evaluable for this endpoint.

Access Abandonment (Permanent Abandonment) will be identified if:

On the EndoAVF Dialysis page, Date endoAVF Successfully Used with 2 Needles for Hemodialysis is not NULL and within a specific visit (e.g., within 395 days for 12 months).

and

On the EndoAVF Abandonment page, Date of Abandonment is not NULL and within a specific visit (e.g. within 395 days for 12 months), the question of "All Possible Attempts Have Been Made to Improve the Condition of the Access" is checked as Yes, and the question of "Could Further Endovascular Interventions

Salvage the Access" is checked as No, and the question of "Could Further Surgical Revisions Salvage the Access?" is checked as No, and Reason for Abandonment is selected as "The Access is No Longer Viable" or "The Access is Viable but there are Complications that Require the Abandonment of the Access".

The binary definition for cumulative functional patency is shown as below:

- If permanent abandonment, as detailed above, occurs on, or before, a specific visit (e.g., 365+30 = Day 395 for 12 months post creation), the participant is considered as having an event (loss of cumulative functional patency).
- If the participant was transferred to PD, or had a kidney transplant, or had access discontinuation, or discontinued before the beginning of a specific visit (e.g., 365-30 = Day 335 for 12 months post creation) without permanent abandonment, the participant is considered not evaluable and will not be included in the analysis.
- Otherwise, if the participant did not have permanent abandonment and has passed the specific visit window by the cutoff date of database lock, the participant is considered as not having an event.

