#### 5.3.6 Interventions

The following endpoints will be conducted on the AT population after the last active treated participant completes their 6-month follow-up; by this time, all participants still in the clinical investigation will have at least 6-months of data.

1) Intervention Post Creation to Facilitate AVF Use

Using the same definition as specified in Section 5.1.2, the number of Facilitation Interventions (On the Post-Procedure Intervention page, Date of Post Procedure Intervention is not NULL and before or on the cutoff date of the database lock, and Type of Intervention is checked as Facilitation) per PY will be estimated by Poisson regression model with only the intercept term, and the estimate and 95% CI will be provided using the Wald method. Additionally, a sensitivity analysis will be completed where the definition of facilitation interventions

is driven by the date of first successful 2-needle cannulation (Date endoAVF Successfully Used with 2 Needles for Hemodialysis on the EndoAVF Dialysis eCRF) where any intervention occurring prior to this date is counted as a facilitation intervention. Note in the event that there are multiple treatments performed during the same procedure driven by multiple reasons, each reason driving the intervention will be counted as a separate intervention.

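### The SAP 5.2.3 event rule for cannulation success names a first-use date with no success condition, unlike its own definition and the field used elsewhere in the SAP

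*SAP*

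**What the plan says.** Protocol 4.2.2 gives cannulation success two parts, a time and a proportion, and both require success: the interval from creation to "first successful use for HD using 2-needle cannulation and proportion of participants with successful first use for HD using 2-needle cannulation". SAP 2.7.2.3 repeats this.

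SAP 5.2.3 keeps the requirement in its definition, "Cannulation success is defined as with successful first use for HD using 2-needle cannulation", and in its Kaplan-Meier time, which runs to "first successful use for HD using 2-needle cannulation through certain post creation visit". Its event rule then reads the EndoAVF Dialysis page and needs only that "Date endoAVF First Used with 2 Needles for Hemodialysis" is present and within the window (Day 210 for the 6-month assessment).

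SAP 5.2.4, the next section, uses a different label on the same eCRF page: "Date endoAVF Successfully Used with 2 Needles for Hemodialysis is not NULL and within a specific visit". SAP 5.3.6 uses that second label too and explains it as the "date of first successful 2-needle cannulation (Date endoAVF Successfully Used with 2 Needles for Hemodialysis on the EndoAVF Dialysis eCRF").

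Below, the two labels are called the First Used date and the Successfully Used date.

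**The concern.** The section that operationalises success is the one place where the field label drops the word. A programmer who follows the event rule literally would record an event on the day two needles were first used, whether or not that use succeeded. If the eCRF holds two dates, three things could follow:

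- The proportion could be too high, because a participant with an attempt but no success counts as an event.
- The time could be too short, because a participant who fails first and succeeds later is dated at the failure.
- Related endpoints could disagree about the same participant, who could be a cannulation success in 5.2.3 and yet never have started successful two-needle dialysis according to 5.2.4.

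The first two errors both flatter the device. Cannulation success is one of three secondary effectiveness endpoints.

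**Working it through.** The plan gives no figure to reproduce here, so the check compares the SAP's rules and follows them through.

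**Step 1: which field each section uses for first two-needle use.**

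| SAP section | Role of the field | Label |
|---|---|---|
| 5.2.3 | Event and event date for cannulation success | First Used |
| 5.2.4 | Part of the event rule; also selects the subset with successful use | Successfully Used |
| 5.3.3 | Classifies the first endoAVF session as two-needle | Successfully Used |
| 5.3.4, 5.3.5 | Selects an additional analysis subset only | Successfully Used |
| 5.3.6, facilitation and maintenance | Date that splits interventions in the sensitivity analyses | Successfully Used |
| 5.3.6, all interventions after first use | Identifies first successful use, where the observation period starts | Successfully Used |
| 5.3.9 | Selects an additional analysis subset | Successfully Used |

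The First Used two-needle label appears only in 5.2.3. The events in 5.3.4 and 5.3.5 are dated from other fields (the start of the 3-week and 28-day periods), so those sections share only the subset rule. Section 5.3.7 does not use the field, and 5.3.8 reaches it only through its reference to 5.2.4.

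**Step 2: the 5.2.3 rule against its definition, assuming two separate fields.**

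| Participant's course | Definition, through Day 210 | Literal 5.2.3 rule, through Day 210 |
|---|---|---|
| First attempt succeeds | Event | Event, same date |
| First attempt fails, later success by Day 210 | Event at the later date | Event at the earlier date |
| First attempt by Day 210 fails, success only after Day 210 | No event | Event |
| Attempt by Day 210 fails, never succeeds | No event | Event |
| No two-needle attempt | No event | No event |

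The second row shortens the time without changing the Day 210 proportion. The third and fourth rows raise that proportion. The fourth also puts a 5.2.3 success outside the subset that 5.2.4 selects by "Date endoAVF Successfully Used with 2 Needles for Hemodialysis is not NULL". In the second and third rows, the 5.2.3 event date also differs from the date that splits facilitation from maintenance interventions in the 5.3.6 sensitivity analyses.

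**Step 3: the same check, assuming one field with two labels.** Every row agrees, and no result changes.

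**Step 4: scale.** The number of participants in rows three and four is not in the documents. For orientation only, each one would add 1/150 = 0.67 percentage points to a crude proportion of the 150 treated participants. With the plan's assumed 20% attrition at 6 months, 150 × 0.80 = 120 remain, and each would add 1/120 = 0.83 points. The planned estimate is Kaplan-Meier, so these are not predictions of its shift.

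**The case against.** The best reply is that there may be only one field. The eCRF and the content of Appendix 2, to which SAP 3.2 defers derivations, are not in the available text. The SAP also gives some sign of using the terms loosely: 5.2.4 describes evaluable participants as those who have started two-needle dialysis, but identifies them by the Successfully Used date. Section 5.3.3 needs the needle type at first use and takes the Successfully Used date for it, where a separate First Used date would have been the natural choice. Success is also stated twice within 5.2.3, so a programmer who reads the whole section has reason not to count a failed attempt.

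These points stand as far as they go. They make a single field plausible but do not show it. On the other side, 5.2.3 prints its label in quotation marks as if copied from the form, and 5.3.3 cites a first-used question for one needle from the same page, so both phrasings may exist there. Neither inference is proof.

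What the reply does not remove is the conflict in the text. The event rule is what gets programmed, and it omits a condition that the definition requires.

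A reader might infer that every section from 5.3.4 to 5.3.9 contradicts 5.2.3. The documents do not support that: as the first table shows, some of those sections use the Successfully Used date only to select a subset, and 5.3.7 not at all.

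**Conclusion.** The inconsistency is real and can be read directly: the 5.2.3 event rule does not carry the success condition of its own definition, and its field label differs from the one used for first two-needle use in the rest of the SAP. Whether any result is at risk depends on one fact that the documents do not give, namely whether the two labels are one eCRF field or two.

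A reader might infer that the plan does count failed cannulations as successes, or might estimate the overstatement by applying an assumed failure rate to the 84.9% six-month figure in protocol 2.1.2. Neither is supported. The first assumes two fields. The second needs a failure rate that appears nowhere in the documents, and the 84.9% is a Kaplan-Meier estimate for the haemodialysis subset of earlier studies, whereas this trial's As-Treated population also includes incident participants.

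The effect is therefore zero if there is one field and of unknown size, in the device's favour, if there are two. Protocol 4.2 and 7.5 make the endpoint descriptive, with no hypothesis test. The primary endpoints, power and type I error are not touched. This is a minor correction, but one worth making.

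**What to change.** First check the EndoAVF Dialysis page of the eCRF for the exact label or labels, and confirm that the Successfully Used date records the first such use, since its label lacks that word. Then amend SAP 5.2.3 so that both the event and its date are defined by the first successful two-needle use, taken from the same field as 5.2.4 and 5.3.6. If the check shows a single field, use its label throughout and state in 5.2.3 that success is required. Make Appendix 2 match.

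The cost is one look at the eCRF, one field name or sentence in the SAP, and the matching line in the derived-data specification. No new data are needed, because the Successfully Used date is already required by other sections. The change should be made before database lock.

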4.4 Applicable Endpoint Definitions

Access Abandonment (permanent abandonment) is defined as the point at which the access can no longer be used for one or two needle prescribed HD as it may be unable to provide adequate flows and / or is deemed unsafe for the participant, and the associated problem cannot be corrected by any further intervention, including medical, surgical, or endovascular interventions or rest.^{8,19} Participants with an abandoned index AVF will continue with follow-up through 24-months and data will be collected on safety and interventions.

A HD AV access is not considered abandoned:

- If the participant discontinues use of the AV access due to kidney transplant, initiation of PD, or participant preference.
- During the maturation period or while waiting for a second stage procedure unless the principal investigator (PI) determines the participant requires and they then receive an alternative HD vascular access.

- During planned interventions, including transposition.
- If all reasonable efforts have not been attempted (and documented) to improve the condition of the access for it to be used.

A discontinuation of use of the clinical investigation AVF for any reason that does not meet this definition of access abandonment will be considered a temporary interruption.

Access Circuit Censoring Events include participant transfer to PD, kidney transplantation or the event of a participants premature discontinuation in the investigation due to withdrawn consent, withdrawal by PI, Lost to Follow-Up (LTF), or participant death (refer to Section 6.5 for definitions).

Adjunctive Procedure(s): Procedure(s) completed during the index procedure (prior to leaving the procedure room) as part of Standard-of-Care (SOC) procedures. These may include procedures to facilitate maturation and / or cannulation of the AVF, procedures to maintain use of the AVF, procedures to ensure HD continuity, as well as procedures to address AFs.

Second Stage Procedure(s): Facilitation Interventions (as defined below) intended to support the cannulation of arterialized vein segments that are determined to be needed a priori to or at the time of the index procedure (i.e. pre-planned facilitation interventions intended to support cannulation). Second stage procedures will not count against the intervention or patency endpoints and will require completion of the Second Stage Procedures eCRF.

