7.5 Secondary Endpoints

The secondary endpoints will be summarized with descriptive statistics (without formal statistical hypothesis testing) using the ITT population for the safety endpoints and the AT population for the effectiveness endpoints. For time-to-event endpoints, the KM production limit method will be used to determine the rate. For categorical variables, summary statistics will include frequency counts and percentages. For rate variables, summary statistics including number of event / PY. For continuous variables, summary statistics will include mean, standard deviation, minimum, median, and maximum. CIs (95%) will be provided using appropriate assumptions based on the variable type. Refer to Section 4.2 for any applicable definitions.

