#### 5.3.4 Functional Maturation

Functional maturation is defined as successful prescribed HD with 2-needle cannulation of the AVF for three (3) continuous weeks.

Functional maturation will be identified if:

On the EndoAVF Dialysis page,

- Date of First 2-needle Cannulation of 3 Week Continuous Dialysis is not NULL and
- Date is before or on the cutoff date of the database lock.

Kaplan-Meier (KM) analysis will be used to estimate the time from HD AV access creation (the date of index procedure) to functional maturation. The following definition will be applied:

- If functional maturation occurs, the participant is considered as having the event, and date of first 2-needle cannulation of 3-week continuous dialysis will be used in the analysis.
- If the participant was transferred to PD, or had a kidney transplant, or had access discontinuation, or discontinued before a specific visit without attaining functional maturation, the participant is considered as censored the participant at the earliest date among these events (i.e. PD start date, kidney transplant date, date of access discontinuation, or last date of available study data including the unscheduled visit date).
- Otherwise, if the participant did not achieve functional maturation and has passed the specific visit window by the cutoff date of database lock, the participant will be censored at the end of the reporting time window (e.g., 180+30 = Day 210 for the 6-month reporting, 730+30 = 760 for the 24-month reporting) for this analysis. If the participant had access permanent abandonment prior to achieving functional maturation and has passed the specific visit window by the cutoff date of database lock, the participant will be censored at the date of permanent abandonment.

This endpoint will be evaluated on the AT population and on the AT population with endo AVF successfully used with 2 needles for hemodialysis (on the EndoAVF Dialysis page, Date endoAVF Successfully Used with 2 Needles for Hemodialysis is not NULL). The number of participants with events, number of participants censored, time to event (days), and proportion of participants with events along with the 95% CI will be presented at 6-weeks, 3-, 6-, 12-, 18-, and 24-months post creation using the KM method. For the 6-month reporting, the functional maturation rate up to 6-months (up to Day 210) will be presented. For the final reporting, the functional maturation rate up to 24-months (up to Day 760) will be presented.

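### Cannulation success is taken from Kaplan-Meier with death, transplant and PD transfer censored, so it overstates the share of participants cannulated; permanent abandonment, also censored, adds to this

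*SAP*

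**What the plan says.** Protocol 4.2.2 and SAP 2.7.2.3 define cannulation success in two parts: the interval from access creation to first successful 2-needle use, and the "proportion of participants with successful first use for HD using 2-needle cannulation", through 6 months.

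SAP 5.2.3 covers both parts with one KM analysis on the As-Treated (AT) population. The "proportion of participants with events along with the 95% CI will be presented at 6-months post creation using the KM method". Its handling of participants without success is:

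- PD transfer, transplant, access discontinuation and study discontinuation are censored at whichever comes first: "If the participant was transferred to PDs, or had a kidney transplant, or had access discontinuation, or discontinued before the end of a specific visit".
- Death is not named, but Protocol 6.5 lists it as a reason for premature discontinuation. Protocol 4.4 also counts it among the access censoring events: "Access Circuit Censoring Events include participant transfer to PD, kidney transplantation", and premature discontinuation through "withdrawal by PI, Lost to Follow-Up (LTF), or participant death".
- After permanent abandonment before first use, "the participant will be censored at the date of permanent abandonment".

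The exploratory endpoints in SAP 5.3.4 (functional maturation: "If the participant was transferred to PD, or had a kidney transplant, or had access discontinuation, or discontinued before a specific visit") and 5.3.5 (functional HD usability) follow the same pattern. Protocol 7.5 sets the general method: "For time-to-event endpoints, the KM production limit method will be used to determine the rate". Neither document plans a cumulative incidence or other competing-risk analysis.

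**The concern.** Censoring in KM assumes that the participant could still have the event later, at the same rate as those who remain under observation. That is reasonable for loss to follow-up or withdrawal of consent. It does not fit a participant who has died, or one whose HD has been replaced by a transplant or PD. KM gives these participants the later success rate of those still at risk. The result is the probability of first use in a setting where nobody dies, is transplanted or moves to PD. It is not the share of treated participants whose fistula was used.

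The direction is fixed. Whenever such an event comes before first use and others are cannulated later, 1 minus KM exceeds the cumulative incidence.

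Permanent abandonment is a plainer case, because it is a failure of the access itself. SAP 5.2.2 counts abandonment before physiological maturation as not having the event and keeps the participant in the denominator. SAP 5.2.3 censors it.

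At stake is the accuracy and the label of a headline secondary effectiveness rate, and of two exploratory rates. All of them err in the favourable direction.

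**Working it through.** The documents give no precision or bias figure for this endpoint, so there is no planned figure to reproduce.

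**Inputs from the documents**

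- Earlier 6-month cannulation success by KM: 84.9%, in the HD subset only (Protocol 2.1.2).
- Earlier mean time to cannulation: 2.0 months (Protocol 2.1.2).
- Treated participants: 150 (SAP 2.4).
- Attrition: 20% by 6 months and 60% by 24 months, pooling loss to follow-up, death and other withdrawals. There is no split by cause, and PD and transplant are not named (SAP 2.4).
- Earlier 6-month cumulative patency: 77.3% (Protocol 2.1.2).

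**Assumptions**

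- q is the six-month risk of death, transplant or PD transfer. The documents do not give it. The range used is 5% to 20%, where 20% would mean that all planned attrition is of this kind.
- 1 minus KM at 6 months is 84.9%, 70% or 50%. The lower values allow for an AT population that includes incident participants not yet on HD.
- Hazards are constant. At 84.9% the cannulation hazard is −ln(0.151)/6 = 0.315 per month, which implies a mean of 2.1 months among those cannulated by month 6. The documents report 2.0.

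**Formula**

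With a = −ln(1 − F)/6, where F is 1 minus KM at 6 months, and b = −ln(1 − q)/6, the cumulative incidence at time T is a/(a+b) × [1 − exp(−(a+b)T)].

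Worked case, F = 84.9%, q = 10%, T = 6: 6a = 1.8905 and 6b = 0.1054. The ratio is 1.8905/1.9958 = 0.9472. The bracket is 1 − 0.151 × 0.9 = 0.8641. The product is 81.8%, so the overstatement is 3.1 points.

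**Results: cumulative incidence (overstatement in points, from unrounded values)**

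| 1 minus KM | q = 5% | q = 10% | q = 15% | q = 20% |
|---|---|---|---|---|
| 84.9% at 6 months | 83.4% (1.5) | 81.8% (3.1) | 80.3% (4.6) | 78.6% (6.3) |
| same hazard, Day 210 (88.6%) | 86.9% (1.7) | 85.2% (3.4) | 83.4% (5.2) | 81.6% (7.1) |
| 70% at 6 months | 68.6% (1.4) | 67.1% (2.9) | 65.6% (4.4) | 64.1% (5.9) |
| 50% at 6 months | 48.9% (1.1) | 47.7% (2.3) | 46.6% (3.4) | 45.4% (4.6) |

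Not every such event comes before first use. In the first row, the share whose competing event comes first is 2.3%, 4.6%, 6.9% and 9.3%.

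**Scale.** The 95% CI half-width at 84.9% with 150 participants, ignoring censoring, is 1.96 × √(0.849 × 0.151/150) = 5.7 points.

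**Abandonment.** The same formula with permanent abandonment as the only competing event and F = 84.9% gives 1.5 points if 5% abandon by 6 months and 3.1 points if 10% do. It gives 7.2 points if the 22.7% implied by the earlier data (100 − 77.3) came at a constant rate. Setting q = 10% together with 10% abandonment gives 5.9 points.

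**Final report.** SAP 5.2.3 also presents the rate to Day 760, which is 760/30.4375 = 24.97 months. As an illustration, take F = 70% at 6 months, constant hazards, and an assumed competing risk of 20% or 30% by 24 months. Then 1 minus KM is 99.3%, against a cumulative incidence of 95.1% or 92.7%. The overstatement is about 4.3 or 6.7 points.

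**The case against.** The strongest reply is that the method is prespecified and answers a sensible question. Protocol 7.5 prescribes KM for time-to-event endpoints, and the endpoint is defined first as an interval. Protocol 4.4 lists PD transfer, transplant and death as censoring events and does not treat transplant or PD as abandonment. The stated objective is whether the device yields a fistula that can be used for HD, so performance among those who still need HD is a defensible target. KM also matches the earlier 84.9%. This justifies keeping the KM curve. It does not make KM estimate the share of participants that the definition names, and it gives no reason to censor abandonment.

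A reader might infer that the SAP departs from the protocol, because the patency definitions in Protocol 4.2.2 refer to censoring events and the cannulation definition does not. The documents do not support that: Protocol 4.4 and 7.5 leave room for what the SAP does.

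A reader might also infer a definite overstatement of 3 to 5 points. That needs a six-month competing risk of about 10% to 15%, and the documents give no such figure. Eligibility requires an expected lifespan of at least 24 months, which argues against many early deaths. The 84.9% comes from the HD subset, and a lower rate in the mixed population would give a smaller bias.

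It is also true that the endpoint is descriptive, that 5.3.4 and 5.3.5 may not be reported at all, and that most of the tabulated differences at 6 months lie within the 5.7-point half-width. SAP 5.2.3 will show the numbers with events and the numbers censored. Those counts are not split by reason, however, so a reader could not rebuild the cumulative incidence from them.

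**Conclusion.** The concern holds as a mismatch between the estimator and the stated proportion, always in the favourable direction. Its size is conditional. For 1 minus KM between 50% and 84.9%, it is about 1 to 2 points at a 5% six-month competing risk, 2 to 3.5 at 10% and 3.5 to 5 at 15%. At the upper end it is about 6 to 7 points if all planned 20% attrition were death, transplant or PD transfer. Loss to follow-up and withdrawal of consent are ordinary censoring and add nothing to this count. Censored abandonment adds bias in the same direction and possibly of similar size.

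These figures rest on constant hazards and on a cause split that the documents do not give. The co-primary endpoints, the type I error and the sample size are untouched. The change is worth making because the rate is a named secondary result and the correction is cheap.

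**What to change.** In SAP 5.2.3, 5.3.4 and 5.3.5:

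- Report the 6- and 24-month proportions, with 95% CIs, as Aalen-Johansen cumulative incidence.
- Treat death, transplant, PD transfer and permanent abandonment before the event as competing events.
- Keep participants with a temporary access discontinuation at risk, since the access may still be used.
- Censor only withdrawal, loss to follow-up and the data cut.
- Keep the KM estimate as a supportive display, labelled as such, for comparison with the earlier rate.
- Tabulate the competing events and the censoring reasons by type.

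The cost is SAP wording and programming, available in SAS 9.4. No new data are needed: the SAP already uses the PD, transplant and abandonment dates, and every death must be reported. The reported rate will be slightly less favourable, and the supportive KM figure covers comparability with the earlier rate.
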